**1. Introduction and Purpose:**

It is standard practice in the United States and many parts of world to perform Gastrointestinal (GI) endoscopy with the patient under deep sedation (1). Obesity is accepted as a patient specific risk factor for hypoxic events during procedural sedation for GI endoscopic procedures. The Obese population has a higher prevalence of obstructive sleep apnea (OSA) which is characterized by repeated obstruction of the upper airway, and leads to apnea and desaturation. This prospective, randomized study was designed to compare the effectiveness of the high flow nasal cannula and the standard nasal cannula in morbidly obese (BMI > 40) patients receiving deep intravenous sedation during colonoscopies. This study will assess whether use of the high flow nasal cannula (HFNC) leads to less intraoperative desaturation events compared to the current standard of care.

**Hypothesis 1-** The HFNC group will have significantly lower incidence of desaturation episodes (SpO2 <90) than the standard nasal cannula group during procedural sedation for colonoscopies.

**Primary objective:** To compare the frequency of desaturation episodes during procedural sedation in obese patients undergoing colonoscopies.

**Hypothesis 2-** The HFNC group will require fewer interventions to treat hypoxic events than the standard nasal cannula group during procedural sedation for colonoscopies.

**Secondary objective1:** To compare the number of interventions made by the anesthesia providers required to treat desaturation events during procedural sedation in patient undergoing colonoscopies.

**Hypothesis 3-** Use of HFNC would decrease sedation-related adverse events in obese subjects with OSA.

**Secondary objective2:** To determine the frequency of desaturation episodes during procedural sedation in obese patients with undiagnosed OSA.

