#### **Outcome Measures:**

- Lowest recorded saturation
- The frequency of desaturation episodes (SpO2 <90%)
- Duration of desaturation episodes (SpO2 <90%)
- Number of apnea episodes
- Dose of propofol or other combination for sedation during colonoscopy
- Anesthesiologist intervention (intubation, airway repositioning, Chin lift)
- Type of airway used (oral airway, nasal airway, bag mask ventilation, suctioning)
- Premature termination of procedure
- Unplanned hospital admission

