## 8. Sources of Research Material:

- Subjects undergoing colonoscopy
- Electronic Medical Record
- Anesthesia Reports
- PHI including name, medical record number, contact information including demographic information including age, gender, race, birth date, weight, height, BMI and medical and surgical history, medication list, ASA classification.
- **Procedural sedation-related variables:** type of sedation agent used for procedural sedation, propofol dose, propofol infusion time, opioid use, any other combination agent for the procedural sedation during colonoscopy, Procedure time, premature termination of procedure.
- **Respiratory event-related variables;** Anesthesiologist intervention (intubation, airway repositioning, Chin lift); Type of airway used (oral airway, nasal airway, bag mask ventilation, suctioning), Laryngospasm or any other airway obstruction; pulse oximetry reading, the number and duration of apnea/hypoxia episodes.
- **Hemodynamic variables** such as baseline blood pressure
- **Postoperative Recovery:** Aldrete score in recovery, the time spend in PACU
- Unplanned hospital admission

- Stop Bang questionnaire for OSA screening

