#### **Risk for HFNC:**

There may be minimal risk for mucosal injury with HFNC. This risk is not higher than standard nasal cannula because HFNC systems deliver heated, humidified gas.

HFNC may produce distending pressure in the lung, similar to CPAP pressures. There may be potentially unpredictable pressures generated by HFNC which may be significant in pediatric but not adult obese population. Mild distending pressure may provide better patent airway in obese subjects. Flow rate of HFNC will be adjusted for maximum benefit to the subject (40-60 L/minutes).

**Psychological Stress:** Some of the questions related to the study may make the subject feel uncomfortable. Subjects may refuse to answer any of the questions, or take a break or stop participation in the study at any time.

**Loss of Confidentiality:** Any time information is collected; there is a potential risk of loss of confidentiality. Every effort will be made to keep your information confidential.

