### **14. Biostatistics:**

The study is powered to detect a 50% reduction in the frequency of desaturation episodes in patients with HFNC compared to patients using a standard nasal cannula. Quadeer et al. (3) reported a 51% incidence rate for desaturation episodes below 90% in patients with standard nasal cannula. Thus to detect a difference of 25% with 80% power and a type 1 error rate of 0.05, the study would need a sample of 59 per group (total n = 118). Assuming a 10% loss of subjects, the total sample size to be enrolled is 130. An interim analysis will be performed at 50% of the enrolment. Based on the interim analysis results, study may be stopped for futility if there is no difference in interim analysis or for early termination for effectiveness if the observed difference at the time is large enough. Obrien-Flemming  $\alpha$ -spending function approach would be used to develop acceptance or rejection boundaries. Continuous data will be summarized using means and standard deviations and categorical data will be summarized using frequencies and percentages. The proportions of desaturation episodes below 90% in the two groups will be compared using a Z test or Fisher's exact test. Mean durations of desaturation episodes and mean numbers of interventions to treat hypoxic events in the two groups will be compared using Student's t-tests or Wilcoxon-Mann-Whitney tests. Frequencies of sedation-related adverse events will be compared using chi-square tests or Fisher's exact tests. Normality of the sample data will be assessed using normal quantile plots. Level of significance will be set at 0.05 and Bonferroni corrections will be made for all primary hypotheses tests.

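### Hypothesis 3, its objective and its test name different endpoints and populations, and HFNC mucosal injury and intolerance are not collected as outcomes

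*Combined protocol and SAP*

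**What the plan says.** All references are to the combined protocol and SAP.

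- **Section 1, Hypothesis 3:** "Use of HFNC would decrease sedation-related adverse events in obese subjects with OSA".
- **Section 1, Secondary objective 2**, placed under that hypothesis: "To determine the frequency of desaturation episodes during procedural sedation in obese patients with undiagnosed OSA". It mentions no comparison of arms.
- **Section 14:** "Frequencies of sedation-related adverse events will be compared using chi-square tests or Fisher's exact tests". The term is not defined there or elsewhere, and the test is not limited to patients with OSA.
- **Section 3, Outcome Measures:** nine items, none labelled as adverse events. The nearest are "Number of apnea episodes", "Premature termination of procedure" and "Unplanned hospital admission". Section 8 adds laryngospasm or other airway obstruction, Aldrete score and PACU time.
- **Sections 3 and 4:** patients are stratified by STOP-BANG, with 5 or more meaning high risk of OSA.
- **Section 10, Risk for HFNC:** "There may be minimal risk for mucosal injury with HFNC". The text goes on to assert that the risk does not exceed that of the standard cannula. Neither the outcome list nor Section 8 includes nasal injury, bleeding or the HFNC flow reached.
- **Section 7** excludes patients who cannot tolerate HFNC because of discomfort. Section 3 randomizes first and fits the cannula afterwards, in the procedure room.

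**The concern.** A hypothesis, its objective and its test should name one endpoint, one population and one comparison. Here they do not, so whoever analyses the trial must choose. One choice restates the primary outcome in a subgroup. The other lets the component events be picked once the results are known. In either case, a reported result for Hypothesis 3 could not be read as a pre-specified answer.

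The device harms are a separate problem, and one that no later analysis can repair. The protocol asserts something about mucosal injury but plans no data that could test it. Intolerance of HFNC during the study can only be seen once the cannula is on, after allocation. Applied at that point, the exclusion removes patients from the HFNC arm alone and removes the harm from the record with them.

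**Working it through.** **1. The three statements side by side**

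| Place | Endpoint | Population | Arm comparison |
|---|---|---|---|
| Hypothesis 3 | sedation-related adverse events | obese, with OSA | implied (HFNC decreases them) |
| Secondary objective 2 | desaturation frequency | obese, undiagnosed OSA | none stated |
| Section 14 test | sedation-related adverse events, undefined | not restricted | yes |

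No two rows agree on all three columns.

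**2. The plan's own figure.** Section 14 gives 59 per group for 51% against a difference of 25 points, 80% power and alpha 0.05. Take p1 = 0.51, p2 = 0.26, mean 0.385:

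n = [1.960 × √(2 × 0.385 × 0.615) + 0.842 × √(0.51 × 0.49 + 0.26 × 0.74)]² / 0.25² = (1.349 + 0.560)² / 0.0625 ≈ 58.3, so 59.

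This reproduces as a two-sided calculation; one-sided would give 46. The plan gives no figure for Hypothesis 3.

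**3. How far the readings differ.** The share of patients with STOP-BANG of 5 or more is not given. As an assumed range I use two background figures: 48.5% screen-positive (Section 2, an endoscopy-centre study) and 64% sleep apnea at BMI over 40 (Section 2). Per arm this is 59 × 0.485 = 28.6 to 59 × 0.64 = 37.8 patients.

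Power = Φ{[d√n − 1.960√(2p̄q̄)] / √(p1q1 + p2q2)}, where d = p1 − p2, p̄ is the mean of the two rates and q = 1 − p. For desaturation in 28.6 per arm: (0.25 × 5.349 − 1.349) / 0.665 = −0.02, giving 49%. The other entries follow the same way. The adverse-event rows assume that HFNC halves the control rate.

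| Reading of Hypothesis 3 | Power |
|---|---|
| Desaturation, 51% v 26%, OSA patients | 49% to 61% |
| Adverse events, OSA patients, control rate 5% | 7% to 8% |
| Same, control rate 10% | 11% to 13% |
| Same, control rate 20% | 18% to 23% |
| Adverse events, all 59 per arm, control rate 5%, 10%, 20% | 11%, 18%, 33% |

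The formula is a normal approximation and is rough at the lowest rates.

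**4. If desaturation is counted as an adverse event.** At the planned rates, OSA patients would contribute 0.51 × 28.6 = 14.6 to 0.51 × 37.8 = 19.3 desaturators on Salter, and 0.26 × 28.6 = 7.4 to 0.26 × 37.8 = 9.8 on HFNC. Other events at an assumed 10% would affect about 2.9 to 3.8 Salter patients. The composite would mostly restate the primary outcome.

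**5. Device harms, if collected in all HFNC patients.** With 0 of 59 affected, the one-sided 95% upper limit is 1 − 0.05^(1/59) = 4.95%. The chance of seeing at least one case, 1 − (1 − p)^59, is 45%, 70% and 95% at true rates of 1%, 2% and 5%. As planned, no estimate is available.

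**The case against.** The strongest reply is that this is a missing definition rather than missing data. Apnea, airway obstruction, early termination and unplanned admission are all recorded, and a test is named. That is correct for the adverse-event endpoint, and it is why the repair is cheap. It does not remove the conflict between hypothesis and objective, and it does not help with mucosal injury or intolerance, which have no outcome or data item.

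A reader might infer that the trial can show benefit but not harm. The documents do not support that. Desaturation, apnea, interventions, laryngospasm, early termination, admission and PACU time could all come out worse on HFNC, and the sample size reproduces as two-sided.

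Three further inferences also fail:

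- **Blood pressure is not collected.** Section 8 refers to haemodynamic variables "such as baseline blood pressure", which is an illustration, and blood pressure is monitored in every patient.
- **Airway pressure is an unmeasured adult risk.** Section 10 says unpredictable pressures may matter in children but not in obese adults.
- **Removing SpO2 below 90% is enough to separate a composite from the primary outcome.** It is not if bag-mask ventilation and intubation remain. Section 3 lists both among the responses to saturation below 90%, and Hypothesis 2 already counts interventions.

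**Conclusion.** The concern holds in two parts. First, Hypothesis 3, Secondary objective 2 and the Section 14 test disagree on endpoint, population and comparison, so the plan does not fix what would confirm or refute the hypothesis. Depending on the reading, power in OSA patients runs from about 7% to about 61%, given the assumed OSA share, event rates and halving. None of these assumptions is needed for the contradiction itself, which is in the text.

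Second, mucosal injury and HFNC intolerance cannot be estimated from the planned data, so the assertion that mucosal risk is no higher with HFNC goes untested. The conclusion is confined to these HFNC-specific harms. It does not extend to safety in general.

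**What to change.** 1. **Align the three statements.** Give Hypothesis 3, Secondary objective 2 and Section 14 the same endpoint, the same population (the existing STOP-BANG stratum of 5 or more) and an HFNC versus Salter comparison. List the component events before any data are seen, using events already collected that are not SpO2 below 90% itself. Laryngospasm or other airway obstruction, premature termination and unplanned admission are examples. State whether apnea is included. Report bag-mask ventilation and intubation under Hypothesis 2, and desaturation in the OSA stratum on a separate line.
2. **Collect the device harms.** Record nasal mucosal injury or bleeding and cannula removal for discomfort in both arms, and the flow reached in the HFNC arm. Report these by randomized arm with confidence intervals and no test.
3. **Reconcile Section 7 with Section 3** so that randomized patients who do not tolerate HFNC are counted in their allocated arm. This concerns who is analysed and does not alter clinical management.

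Cost: revised wording in a few sections and a few data fields. The adverse-event endpoint will have few events and low power, especially in the OSA stratum, so it should be presented as an estimate with an interval and that limit stated in advance.

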**2. Background:**

The prevalence of morbid obesity is increasing worldwide. As the severity of obesity increases, the incidence of diagnosed obstructive sleep apnea also rises. Studies have shown an incidence of sleep apnea as high as 64% in patients with a body mass index (BMI) over 40 and 100% in patients with a BMI greater than 60 (2). Patients with OSA have been shown to have significant desaturations under intravenous sedation due to airway narrowing and obstruction. Several studies have also shown that morbidly obese subjects, independent of a diagnosis of OSA, run a higher perioperative risk of adverse

airway events, including hypoxia. Quadeer et al found a 51% overall incidence of desaturation below 90% in a prospective observational study with 79 patients undergoing endoscopy under “conscious sedation.” They also found a significant difference in the frequency of desaturation events between obese (BMI > 30) and non-obese patients (3). Many morbidly obese subjects present to our institution for GI procedures under deep sedation. Providing anesthesia for this patient population is challenging and requires careful titration of drugs and superb airway management skills.

The current standard of care for oxygen delivery in this setting is a Salter nasal cannula. There are no prospective, randomized studies that compare the use of a high flow humidified nasal cannula system and standard nasal cannula in morbidly obese patients presenting for colonoscopy under anesthesia. Patel et al have been working with a transnasal high flow device (THRIVE) and have shown it to increase apnea times in patients with difficult airways post induction of general anesthesia (4). These patients received neuromuscular blockade and made no respiratory effort, however, the patency of their airway was maintained with a manual jaw thrust by anesthesia providers. They concluded that the device combines the benefits of apneic oxygenation with continuous positive airway pressure and gaseous exchange occurs through flow-dependent dead space flushing (5).

Humidified high flow nasal cannula (HFNC) oxygen therapy utilizes an air oxygen blend allowing from 21% to 100% FiO2 delivery and generates up to 60 L/min flow rates (6,7). The gas is heated (35 to 40 degree Celsius) and humidified through an active heated humidifier and delivered via a single limb heated inspiratory circuit (to avoid heat loss and condensation) to the subject through a large diameter nasal cannula (8, 9). Theoretically, HFNC offers significant advantages in oxygenation and ventilation over conventional methods (9). Constant high flow oxygen delivery provides steady inspired oxygen fraction (FiO2) and decreases oxygen dilution (10). It also washes out physiologic dead space and generates positive end expiration pressure (PEEP) that augments ventilation (10, 11). In the current narrative review, Sotello et al. summarized factors explained the improvement in respiratory parameters by using HFNC (12). (1) Washout of the nasopharyngeal dead space; (2) Reduction in inspiratory resistance associated with gas flow through the nasopharynx; (3) Improvement in respiratory mechanical parameters associated with gas temperature and state of humidification; (4) Reduction in metabolic work associated with gas conditioning; (5) Provision of mild distending pressure.

Some studies have demonstrated a positive effect of HFNC on the apnea-hypopnea index (AHI) showing that use of HFNC could decrease hypoxic episodes in subjects with repetitive upper airway obstruction such as obstructive sleep apnea. The STOP-BANG questionnaire (SB) has been used successfully to screen patients undergoing therapeutic endoscopic procedures at higher risk for sedation-related adverse events (14). Mehta et al (15) evaluated the prevalence of undiagnosed OSA at their endoscopy center and the relationship between a positive SB result and sedation-related adverse events. They found that 48.5% (118/243) of patients were SB+ and exhibited a higher level of potentially adverse medical conditions, with 66.3% (161/243) being classified with an SB score of 3.

We are hypothesizing that the HFNC will help maintain a patent airway and improve gaseous exchange in the morbidly obese patients undergoing deep sedation for colonoscopies and will result in a significant decrease in intraoperative desaturation events, thus improving morbidity and overall safety for this subgroup.

**3. Concise Summary of Project:** The study population for this randomized prospective clinical trial will consist of male and female subjects, between the ages of 18-80, with a BMI over 40 undergoing colonoscopies. Consent will be obtained by research coordinator or anesthesia providers involved in

the study. OSA screening questionnaire (Stop Bang) will be completed during review of the patient's history and physical exam and subjects will be stratified based on STOPBANG score of  $\geq 5$  versus  $\leq 4$ . Subjects will then be randomized in a stratified fashion to either the HFNC (Comfort Flo System) group or the Salter cannula group. Then subjects will be brought into the procedure room and placed on all standard ASA monitors (BP cuff, EKG, pulse oximetry). In the HFNC group, the nasal cannula will be placed on the patient at a setting of FiO2 36% and up to 60L/min depending on patient tolerance. 60 L/min is the max flow rate and will be used as tolerated for maximum benefit. The HFNC setting will start at 40 L/min and will be titrated up to the max flow rate of 60 L/min depending on subjects' tolerance.

**Research intervention:** The Comfort Flo system (Teleflex Medical, Research Triangle Park, NC, USA) will be used for high flow nasal cannula during colonoscopy. The Comfort Flo System has an air-O2 blender setting and a FiO2 analyzer to confirm FiO2 delivered to the patient. This FiO2 has been shown to be equal to the FiO2 measured using the Salter cannula at 4L/min (13).

Control group: A Salter nasal cannula will be used at 4L/ minute during the colonoscopy.

The cannulas will be placed on the patients 5 minutes prior to the start of the anesthetic.

All patients will receive a similar intravenous anesthetic with a propofol infusion titrated to a Richmond Agitation-Sedation Scale (RASS) score of 3-4. A lidocaine bolus of up to 100 mg can be used prior to the start of the propofol infusion for initial tolerance of the drug. Patient saturation is recorded every minute during the anesthetic on the electronic medical record and is available for review. The duration and frequency of all measurements at or below 90% will be recorded by the Electronic Medical Record (EMR). The anesthesia providers will be instructed to intervene only when the patient's saturation falls below 90%, by either manually performing a jaw thrust, placing a nasal or oral airway, bag mask ventilation, increasing the patients FiO2 or decreasing the rate/ pausing the propofol infusion or endotracheal intubation. They will be instructed to write a quick note at the time of intervention in the EMR describing their maneuver. Duration of the study will be the length of the procedure through discharge from the Postoperative Anesthesia Care Unit (PACU).

Our hypothesis is that the patients in the high flow nasal cannula group will experience a marked reduction in intraoperative desaturation events as compared to the Salter cannula group.

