#### **4. Study Procedures:**

- OSA screening with the SB questionnaire: SB is made up of 8 yes or no questions (14). The anesthesiologist or certified registered nurse anesthetist will be blinded to the results of the SB.

High risk of obstructive sleep apnea if yes to  $\geq 5$  questions; low risk of obstructive sleep apnea: yes to  $\leq 4$  questions.

- Randomization to the high flow nasal cannula group or the Salter cannula group. Subjects will be randomized in a 1:1 ratio according to a computer generated randomization list provided by the study statistician.
- All standard monitoring (BP, EKG, pulse oximeter) placed on all patients in the procedure room. Cannulas placed on the patients 5 minutes prior to the start of the anesthetic and set to rate of 4/min for standard nasal cannula and 36% FiO2 up to 60 L/min for the HFNC group.
- Anesthesia achieved with a propofol infusion titrated to a RAS score of 3-4.
- All desaturation points at or below 90% recorded via intraoperative electronic charting (Epic).
- Frequency and method of intervention aimed at increasing the patient's saturation by the provider will be recorded on the EMR at the time of intervention with a quick note.

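### Randomisation is stratified by STOP-BANG (≥5 v ≤4), but the planned tests ignore the stratum, and the adverse-event test is not restricted to the OSA group that Hypothesis 3 concerns

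*Combined protocol and SAP*

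**What the plan says.** **Design.** Section 3 (Concise Summary of Project) says "subjects will be stratified based on STOPBANG score of" ≥5 versus ≤4, and then "Subjects will then be randomized in a stratified fashion". Section 4 (Study Procedures) repeats the cut-point as a risk label ("High risk of obstructive sleep apnea if yes to" five or more questions). It describes the allocation only as 1:1 from a computer-generated list.

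**Analysis.** Section 14 (Biostatistics) gives the primary test: "The proportions of desaturation episodes below 90% in the two groups will be compared using a Z test or Fisher's exact test". Durations and intervention counts get t-tests or Wilcoxon-Mann-Whitney tests. For adverse events: "Frequencies of sedation-related adverse events will be compared using chi-square tests or Fisher's exact tests". Section 14 mentions no stratum, covariate, subgroup, interaction, STOP-BANG score or OSA.

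**OSA question.** Section 1 states Hypothesis 3 as "Use of HFNC would decrease sedation-related adverse events in obese subjects with OSA". The objective paired with it is "To determine the frequency of desaturation episodes during procedural sedation in obese patients with undiagnosed OSA".

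**The concern.** There are two separate issues.

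1. The design balances the arms on a baseline factor, and the analysis then leaves it out. The Background treats the factor as prognostic: it says that patients with OSA desaturate under sedation and that STOP-BANG picks out patients at higher risk of sedation-related events. If so, the plan gives up some precision that it could have for free.

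2. Hypothesis 3 compares the arms on adverse events in patients with OSA. The only adverse-event test in Section 14 carries no such restriction, so following the plan literally tests all patients. The paired objective differs in outcome (desaturation), in group (undiagnosed OSA) and in kind (descriptive, with no comparison of arms). The reported result could come from all patients, from the ≥5 stratum or from a group defined by diagnosis. These answer different questions, and nothing says which was chosen before the data were seen.

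**Working it through.** **Step 1. Reproduce the planned sample size.** Inputs from Section 14: 51% control rate, 25-point difference (so 26% on HFNC), 80% power, type I error 0.05. Two-sided is assumed, since the plan does not say. With p̄ = 0.385:

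n = [1.96·√(2·0.385·0.615) + 0.842·√(0.51·0.49 + 0.26·0.74)]² / 0.25² = [1.349 + 0.560]² / 0.0625 ≈ 58.3, so 59 per group.

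This matches the plan. Power at 59 per arm is 80.5%. The figure belongs to the whole-sample Z test only; Fisher's exact test, the other option in Section 14, has 74.9% power at the same n.

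**Step 2. Why the Z test is conservative when the stratum matters.** The pooled variance includes variation between strata, which balanced allocation has already removed. Take half the patients at ≥5 and a stratum odds ratio of 3.5, which gives control rates of 66% and 36%. Under no treatment effect:

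- variance used by the Z test: 0.51·0.49 = 0.2499
- average variance within strata: (0.66·0.34 + 0.36·0.64)/2 = 0.2274
- ratio 0.91, so the true standard error is √0.91 = 0.954 of the one used
- the effective critical value is 1.96/0.954 = 2.05, a two-sided level of about 4%

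**Step 3. Simulated size of the effect.** 200,000 trials per scenario; 59 per arm; overall rates 51% v 26%; common treatment odds ratio; shares at ≥5 of 30%, 50%, 64% and 75%; arms within a stratum differing by at most one patient; CMH without continuity correction. Shares and stratum odds ratios are assumptions. The 64% is the sleep-apnea figure that the Background cites for BMI over 40, not a STOP-BANG rate.

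| Stratum odds ratio | Power forgone by Z v CMH (points) |
|---|---|
| 1 | −0.1 to −0.2 (CMH slightly lower) |
| 2 | 0.4 to 0.6 |
| 3 | 1.1 to 1.7 |
| 3.5 | 1.4 to 2.4 |

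Z-test power is 80.4% to 81.5% throughout. At odds ratio 3.5 the type I error is 4.3% to 4.5% for Z and 4.9% for CMH. If balance within strata is not enforced and the stratum is not prognostic, CMH is about 0.5 points lower.

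A different model, with HFNC halving the rate in each stratum, points the same way. At a 40-point gap between strata (for example 71.6% v 31.6%, an odds ratio of about 5.5), Z has a type I error of about 3.5% and CMH gains 2.4 to 2.7 points.

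**Step 4. What the ≥5 stratum can show.** For desaturation at the planned effect, n per arm = 59 × share, half-width = 1.96·√[(pc(1−pc) + pt(1−pt))/n], and power uses the pooled-variance formula. Example at a 50% share and odds ratio 1 (n = 30): half-width = 1.96·√(0.4423/30) = 0.238; power = Φ[(0.25·√30 − 1.349)/0.665] = Φ(0.03) = 51%. Over odds ratios 1 to 3.5:

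| Share at ≥5 | n per arm | 95% CI half-width (points) | Power |
|---|---|---|---|
| 30% | 18 | 31 | 33–39% |
| 50% | 30 | 24 | 51–61% |
| 64% | 38 | 21–22 | 61–70% |
| 75% | 44 | 20 | 68–75% |

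The whole-sample half-width is 1.96·√(0.4423/59) = 17 points. The treatment-by-stratum interaction has a half-width of about 33 to 39 points, roughly twice that.

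The documents give no adverse-event rate. At assumed rates of 5% to 30%, 1.96·√(2p(1−p)/n) gives 14 to 30 points with 18 per arm and 9 to 19 with 44.

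**The case against.** **The primary-test issue is close to a preference.** The Z test is valid, the gain from CMH is under 1 point at odds ratio 2, and it reverses at 1. The documents give no odds ratio. The Background also says that airway risk is raised in morbid obesity whether or not OSA is diagnosed, so a weak stratum effect is plausible. All of this stands, and it is why the change is offered as a cheap improvement. A reader might infer that ignoring the stratum inflates the type I error or costs the trial its planned power. Neither follows: the error moves down as the stratum becomes prognostic, and power stays at about 80%. The open choice between the Z test and Fisher's exact test matters more, at 80.5 − 74.9 = 5.6 points.

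**Hypothesis 3 does have a population.** A reader might infer that none is stated. That goes too far. Section 1 names obese subjects with OSA, Sections 3 and 4 fix the ≥5 cut-point in advance, and the Background cites a study that approached undiagnosed OSA through STOP-BANG positivity, which suggests the intended proxy. Nor does Secondary objective 2 need a test: it is descriptive, and Section 14 provides that "categorical data will be summarized using frequencies and percentages". What remains is the missing link. No text ties the ≥5 group to the adverse-event test or to the objective. The score alone cannot identify undiagnosed OSA either, since Section 7 does not exclude diagnosed OSA and the Background says that diagnosed OSA rises with obesity.

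**The adverse events can be worked out.** The Outcome Measures in Section 3 and the variables in Section 8 list candidates such as apnea, laryngospasm, intubation and early termination. That is fair: defining the composite is a supporting clarification.

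**Conclusion.** The point holds in two parts of unequal weight.

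The analysis ignores the randomisation stratum. This leaves the primary test valid and slightly conservative. The power forgone is roughly 0 to 2.4 points for stratum odds ratios of 1 to 3.5 and shares at ≥5 of 30% to 75%. Both ranges are assumed, and the figures apply to the Z test only.

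The more substantive part is Hypothesis 3. Its OSA group is named in words but not tied operationally to any analysis, so the adverse-event test as written would answer for all patients. Even when correctly restricted, the ≥5 stratum has only about 33% to 75% power for the planned desaturation effect. A null result there should not be read as absence of benefit in patients at high OSA risk.

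**What to change.** **1. Use the stratum (cheap improvement).** In Section 14, replace the choice between the Z test and Fisher's exact test with one primary analysis: a CMH test stratified by STOP-BANG ≥5 v ≤4, with a stratum-adjusted risk difference and 95% CI. Use the same statistic at the interim look. Use stratified versions for the secondary comparisons, for example a van Elteren test for durations and intervention counts and CMH for adverse events. The sample size does not change. The cost is analysis wording, plus about 0.1 to 0.5 points of power if the stratum turns out not to be prognostic.

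**2. Tie Hypothesis 3 to a group.** State that it is analysed in the ≥5 stratum, described as high OSA risk and not as diagnosed OSA. Report the arm difference with a 95% CI and a treatment-by-stratum interaction estimate, both labelled exploratory. Use the same ≥5 stratum for Secondary objective 2, so that hypothesis and objective share one population. Report the subset with no prior OSA diagnosis descriptively only. Acknowledge that patients with diagnosed OSA who score ≤4 fall outside this group.

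**3. Supporting clarification.** Before outcomes are seen, list which of the variables in Sections 3 and 8 count as sedation-related adverse events.

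Items 2 and 3 need a wording amendment to Sections 1, 3 and 14. No new data are needed: the score is obtained before randomisation, and medical history and respiratory events are already collected under Section 8.
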